10.1.4 Pregnancy reporting

Reproductive toxicity and teratogenicity data are not available for the investigational drug at this time; therefore, no guidelines on therapeutic recommendations in case of pregnancy are available. This study enrolls women who are of non-child-bearing potential, thus pregnancy is not an expected outcome for any female study participant. However, in the case that a pregnancy in a female study participant should occur, please follow the below reporting guidelines.

To ensure subject safety, each pregnancy occurring after signing the informed consent must be reported to Novartis within 24 hours of learning about its occurrence. The pregnancy should be followed up to determine outcome, including spontaneous or voluntary termination, details of the birth, and the presence or absence of any birth defects, congenital abnormalities, or maternal and/or newborn complications.

Pregnancy should be recorded and reported by the investigator to the Novartis Chief Medical Office and Patient Safety (CMO&PS). Pregnancy follow-up should be recorded on the same form and should include an assessment of the possible relationship to the study treatment. Any SAE experienced during pregnancy must be reported.

The study drug must be discontinued, though the subject may stay in the study, if she wishes to do so. All assessments that are considered as a risk during pregnancy must not be performed. The subject may continue all other protocol assessments.

Pregnancy outcomes should be collected for the female partners of any males who took study treatment in this study. Consent to report information regarding these pregnancy outcomes should be obtained from the mother.

Pregnancy outcomes will be followed-up at the following times:

- 12 months after the estimate date of delivery (for a live birth only)

10.1.5 Reporting of study treatment errors including misuse/abuse

Medication errors are unintentional errors in the prescribing, dispensing, administration or monitoring of a medicine while under the control of a healthcare professional, subject or consumer (EMA definition).

Misuse refers to situations where the medicinal product is intentionally and inappropriately used not in accordance with the protocol.

Abuse corresponds to the persistent or sporadic, intentional excessive use of a medicinal product, which is accompanied by harmful physical or psychological effects.

Study treatment errors and uses outside of what is foreseen in the protocol will be recorded on the appropriate eCRF irrespective of whether they are associated with an AE/SAE. Errors will be reported to Safety only if associated with an SAE. Misuse or abuse will be collected and reported in the safety database irrespective of it being associated with an AE/SAE within 24 hours of Investigator's awareness.

Table 10-1 Guidance for capturing the study treatment errors including misuse/abuse

Treatment error type	Document in Dosing eCRF (Yes/No)	Document in AE eCRF	Complete SAE form
Unintentional study treatment error	Yes	Only if associated with an AE	Only if associated with an SAE
Misuse/Abuse	Yes	Yes	Yes, even if not associated with a SAE

For more information on AE and SAE definition and reporting requirements, please see [Section 10.1](#).

10.2 Additional Safety Monitoring

10.2.1 Liver safety monitoring

To ensure subject safety and enhance reliability in determining the hepatotoxic potential of an investigational drug, a standardized process for identification, monitoring and evaluation of liver events must be followed.

The following two categories of abnormalities / adverse events have to be considered during the study (irrespective of whether classified/reported as AE/SAE):

- Liver laboratory triggers, which will require repeated assessments of the abnormal laboratory parameter
- Liver events, which will require close observation; follow-up monitoring and contributing factors are recorded on the appropriate eCRFs

Please refer to [Table 16-1](#) in Appendix 2 for complete definitions of liver laboratory triggers and liver events.

Every liver event defined in [Table 16-1](#) should be followed up by the investigator or designated personnel at the trial site, as summarized below. Additional details on actions required in case of liver events are outlined in [Table 16-2](#). Repeat liver chemistry tests (i.e., ALT, AST, TBL, PT/INR, ALP and γ -GT) to confirm elevation.

- These liver chemistry repeats should be performed by the site's local laboratory. Repeated laboratory test results must be reported as appropriate.
- If the initial elevation is confirmed, close observation of the subject will be initiated, including consideration of treatment interruption if deemed appropriate.
- Discontinuation of the investigational drug (refer to [Section 9.1.1](#)), if appropriate
- Hospitalization of the subject, if appropriate
- Causality assessment of the liver event
- Thorough follow-up of the liver event should include, based on the investigator's discretion:
 - Serology tests, imaging and pathology assessments, hepatology consultation, obtaining more detailed history of symptoms and prior or concurrent diseases, history of concomitant drug use, exclusion of underlying liver disease

All follow-up information and procedures performed must be recorded as appropriate in the eCRF.

Refer to the SOM for additional details.

10.2.2 Renal safety monitoring

Every renal laboratory trigger or renal event must be followed up by the investigator or designated personnel at the trial site.

All follow-up information, and the procedures performed must be recorded as appropriate in the eCRF. Refer to the SOM for additional details.

11 Data Collection and Database management

11.1 Data collection

Designated investigator staff will enter the data required by the protocol into the Electronic Case Report Forms (eCRF). The eCRFs have been built using fully validated secure web-enabled software that conforms to 21 CFR Part 11 requirements. Investigator site staff will not be given access to the EDC system until they have been trained. Automatic validation programs check for data discrepancies in the eCRFs and allow modification and/or verification of the entered data by the investigator staff.

The investigator/designee is responsible for assuring that the data recorded on eCRFs is complete, accurate, and that entry and updates are performed in a timely manner. The Investigator must certify that the data entered are complete and accurate.

After final database lock, the investigator will receive copies of the subject data for archiving at the investigational site.

Automatic validation programs check for data discrepancies, and, by generating appropriate error messages, allow the data to be confirmed or corrected before transfer to the vendor working on behalf of Novartis.

All data should be recorded, handled, and stored in a way that allows its accurate reporting, interpretation, and verification.

11.2 Database management and quality control

Novartis personnel (or designated CRO) will review the data entered by investigational staff for completeness and accuracy. Electronic data queries stating the nature of the problem and requesting clarification will be created for discrepancies and missing values and sent to the investigational site via the EDC system. Designated investigator site staff are required to respond promptly to queries and to make any necessary changes to the data.

Concomitant treatments and prior medications entered into the database will be coded using the World Health Organization (WHO) Drug Reference List, which employs the Anatomical Therapeutic Chemical classification system. Medical history/current medical conditions and adverse events will be coded using the Medical Dictionary for Regulatory Activities (MedDRA) terminology.

At the conclusion of a non-IRT study, the occurrence of any emergency code breaks will be determined after return of all code break reports and unused supplies to Novartis.

Once all the necessary actions have been completed and the database has been declared to be complete and accurate, it will be locked, **and the treatment codes will be unblinded** and made available for data analysis/moved to a restricted area to be accessed by an independent programmer and statistician. Any changes to the database after that time can only be made after written agreement by Novartis development management.

11.3 Site monitoring

Before study initiation, at a site initiation visit or at an investigator's meeting, a Novartis representative will review the protocol and data capture requirements (i.e., eSource DDE or eCRFs) with the investigators and their staff. During the study, Novartis employs several methods of ensuring protocol and GCP compliance and the quality/integrity of the sites' data. The field monitor will visit the site to check the completeness of subject records, the accuracy of data capture/data entry, the adherence to the protocol and to GCP, the progress of enrollment, and to ensure that study treatment is being stored, dispensed, and accounted for according to specifications. Key study personnel must be available to assist the field monitor during these visits. Continuous remote monitoring of each site's data may be performed by a centralized Novartis CRA. Additionally, a central analytics organization may analyze data & identify risks & trends for site operational parameters and provide reports to Novartis clinical teams to assist with trial oversight.

The investigator must maintain source documents for each subject in the study, consisting of case and visit notes (hospital or clinic medical records) containing demographic and medical information, laboratory data, electrocardiograms, and the results of any other tests or assessments. All information on eCRFs must be traceable to these source documents in the subject's file. The investigator must also keep the original informed consent form signed by the subject (a signed copy is given to the subject).

The investigator must give the monitor access to all relevant source documents to confirm their consistency with the data capture and/or data entry. Novartis monitoring standards require full verification for the presence of informed consent, adherence to the inclusion/exclusion criteria, documentation of SAEs, and of data that will be used for all primary variables. Additional checks of the consistency of the source data with the eCRFs are performed according to the study-specific monitoring plan. No information in source documents about the identity of the subjects will be disclosed.

12 Data analysis and statistical methods

The statistical analysis will be carried out after end of study and data base lock. Any data analysis carried out independently by the investigator should be submitted to Novartis before publication or presentation.

12.1 Analysis sets

For all analysis sets, subjects will be analyzed according to the study treatment(s) received.

The safety analysis set will include all subjects that received any study drug.

The PK analysis set will include all subjects with at least one available valid (i.e., not flagged for exclusion) PK concentration measurement, who received any study drug and with no protocol deviations that impact on PK data.

The PD analysis set will include all subjects with available PD data and no protocol deviations with relevant impact on PD data.

12.2 Subject demographics and other baseline characteristics

Demographic and other baseline data including OA severity by KLG will be listed for all subjects and summarized descriptively by LRX712 and placebo treated groups using the Safety set.

Categorical data will be presented as frequencies and percentages. For continuous data, mean, standard deviation, median, minimum, and maximum will be presented. For highly skewed continuous data, mean and standard deviation will not be presented. For selected parameters, 25th and 75th percentiles may also be presented.

Relevant medical histories and current medical conditions at baseline will be listed by treatment group and subject.

12.3 Treatments

Data for study drug administration and concomitant therapies will be listed by subject and treatment group.

12.4 Analysis of the primary endpoint(s)

12.4.1 Definition of primary endpoint(s)

Change in cartilage volume in the index region measured by 7T MRI from baseline to week 28 in LRX712- vs. placebo-treated subjects.

12.4.2 Statistical model, hypothesis, and method of analysis

It is hypothesized that LRX712 treatment will increase the cartilage volume of the impacted compartment from its baseline level, and that this change will be detectable using 7T MRI. For the primary analysis, the signal intensity (measured as an absolute change from baseline) will be analyzed using a Mixed effect Model with Repeated Measures (MMRM). The model will include treatment, time, treatment*time as fixed effects. An unstructured matrix will be used to model within-subject correlation. The signal intensity in pre-defined cartilage sub-regions of the different knee compartments may be, if needed, logarithmically transformed prior to analysis.

Least squares means of the treatment difference will be reported together with two-sided 90% confidence intervals. Analysis of the primary endpoint will be done at week 28 separately for LRX712 15mg vs. Placebo and LRX712 25mg vs. Placebo.

12.4.3 Handling of missing values/censoring/discontinuations

Missing values of the primary endpoint (cartilage volume at week 28) will be treated as missing at random and imputed by the MMRM.

12.4.4 Sensitivity and Supportive analyses

Supportive analyses which explore the treatment effect of pooling data from all subjects dosed with LRX712 together may be done following the same method described in [Section 12.4.2](#). No adjustment for multiplicity is planned for this supportive analysis.

12.5 Analysis of secondary endpoints

12.5.1 Efficacy and/or Pharmacodynamic endpoint(s)

The secondary PD endpoints (i.e., cartilage [^{23}Na] content, volume and thickness at weeks 16 and 52) will be analyzed in the same manner as the primary endpoint, by MMRM with an unstructured covariance matrix. The cartilage volume and thickness will both be analyzed on their original scales.

12.5.2 Safety endpoints

For all safety analyses, the safety set will be used. All listings and tables will be presented by treatment group.

Adverse events

The number (and percentage) of subjects with treatment emergent adverse events (events started after the first dose of study medication or events present prior to start of double-blind treatment but increased in severity based on preferred term) will be summarized in the following ways:

- by treatment, primary system organ class and preferred term.
- by treatment, primary system organ class, preferred term and maximum severity.
- by treatment, Standardized MedDRA Query (SMQ) and preferred term.

Separate summaries will be provided for study medication-related adverse events, deaths, serious adverse events, or other significant adverse events leading to discontinuation.

A subject with multiple adverse events within a primary system organ class is only counted once towards the total of the primary system organ class.

To assess local tolerability of LRX712 with multiple injections, the probability of an injection site adverse event will be calculated for each treatment group. A Bayesian Poisson regression model will be fitted with treatment group as fixed categorical variable. Further details on the definition of injection site adverse events is given in the SAP.

Vital signs

All vital signs data will be listed by treatment group, subject, and visit/time, and if ranges are available, abnormalities (and relevant orthostatic changes) will be flagged. Summary statistics will be provided by treatment and visit/time.

12-lead digitized ECG

A standard 12-lead electrocardiogram will be performed in triplicate:3 tracings of at least 10 sec duration to be obtained within a 2-5 min window). A standard 12-lead electrocardiogram will be performed in triplicate (3 tracings of at least 10 sec duration to be obtained within a 2-5 min window.

1. PR, QRS, QT, QTcF, and RR intervals will be obtained from 12-lead ECGs for each subject during the study. ECG data will be read and interpreted locally.
2. Categorical Analysis of QT/QTc interval data based on the number of subjects meeting or exceeding predefined limits in terms of absolute QT/QTc intervals or changes from baseline will be presented. In addition, a listing of these subjects will be produced by treatment group.

All ECG data will be listed by treatment group, subject and visit/time; abnormalities will be flagged. Summary statistics will be provided by treatment and visit/time.

Clinical laboratory evaluations

All laboratory data will be listed by treatment group, subject, and visit/time and if normal ranges are available abnormalities will be flagged. Summary statistics will be provided by treatment and visit/time. Shift tables using the low/normal/high/ classification will be used to compare baseline to the worst on-treatment value. A longitudinal representation of the data will be presented if deemed necessary.

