1.3 Clinical data

1.3.1 Human safety and tolerability data

The completed first-in-human study enrolling 42 subjects with early to moderate OA (KLG 1-3) evaluated the safety, tolerability and pharmacokinetic profile of single injections of LRX712 microcrystals (at doses from 0.5 to 75 mg, 7 groups of 6 subjects each, with randomization ratio 4:2 between LRX712 and placebo) into the knee. Two sentinel subjects (LRX712: placebo = 1:1) were dosed first in each cohort, and their safety data were reviewed before dosing the remaining 4 subjects. LRX712 was safe up to single 75 mg i.a. injection in subjects with OA. Injection site tolerability reactions were less frequent and milder in lower dose groups compared to the 40 and 75 mg dose groups, where 75% and 100% of subjects, respectively, reported any adverse injection site reaction. Of those, (3/4 subjects reported moderate reactions in the 40 mg group and 2/4 in the 75 mg group). A total of 29 subjects (69.0%) consisting of more than 75% of subjects in the LRX712 treatment groups (25 subjects) and 4 subjects (28.6 %) in the placebo group had AEs suspected to be related to the study drug by the Investigator. All subjects in the treatment groups LRX712 7.5 mg, LRX712 25 mg, LRX712 40 mg, LRX712 75 mg had AEs suspected to be related to the study drug by the Investigator. The most frequent AEs were injection site warmth, discomfort or pain, or related terms. . **CCI**

All subjects exposed to LRX712 reported at least one AE. However, there were no SAEs, AE-related discontinuations, or death. None of the AEs posed a systemic safety signal.

CCI

As a result, the study was put on temporary hold while further investigations were initiated. **CCI** from the FIH study also identified a pattern of transient (< 5 days duration) elevations in hsCRP post-administration, increasing with LRX712 dose levels > 15 mg, consistent with observed during acute respiratory illness, for example, hsCRP elevations Pathologic values ranged from 5-57.5 mg/L (mean 12.8 mg/L, median 8.4 mg/L).

[figure not shown]

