#### **5.1 Adverse event (AEs)**

All information obtained on adverse events will be displayed by treatment and participant.

The number (and percentage) of participants with treatment emergent adverse events (events started after the first dose of the study medication or events prior to start of the treatment but increased in severity based on the preferred term) will be summarized by treatment, primary system organ class and preferred term, and maximum severity.

Separate summaries will be provided for study medication related adverse events, death, serious adverse events, other significant adverse events leading to discontinuation.

A participant with multiple adverse events within a primary system organ class is only counted once towards the total of the primary system organ class.

If, for the same participant, several consecutive AEs (irrespective of start treatment causality, seriousness and severity) occurred with the same SOC and PT:

- A single occurrence will be counted if there is  $\leq 1$  day gap between the end date of the preceding AE and the start date of the consecutive AE.
- More than one occurrence will be counted if there is  $> 1$  day gap between the end date of the preceding AE and the start date of the consecutive AE.

For occurrence, the presence of at least one SAE has to be checked in a block e.g. among AEs in a  $\leq$  day gap block. If at least one SAE is occurring, then one occurrence is calculated for that SAE.

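### Protocol 12.5.2 asks for a per-arm probability of an injection-site AE but specifies a Poisson count model, and the readable SAP supplies neither the event definition nor the model

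*Protocol*

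**What the plan says.** Local tolerability of repeated injections is a secondary objective (Protocol Table 2-1, SAP 1.3). For it, Protocol 12.5.2 states that "the probability of an injection site adverse event will be calculated for each treatment group". The method is given in one sentence: "A Bayesian Poisson regression model will be fitted with treatment group as fixed categorical variable". The event itself is deferred: "Further details on the definition of injection site adverse events is given in the SAP". The same section also plans a grouped AE summary "by treatment, Standardized MedDRA Query (SMQ) and preferred term".

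SAP 5.1 plans general AE tables only: participants with treatment-emergent events "will be summarized by treatment, primary system organ class and preferred term, and maximum severity". Its occurrence rule concerns the case where, in one participant, "several consecutive AEs (irrespective of start treatment causality, seriousness and severity) occurred with the same SOC and PT": such events are merged if the gap is at most one day and counted separately otherwise. Nothing readable in SAP Section 5 defines an injection-site AE, names a Poisson or other model for it, or mentions an SMQ table.

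SAP Section 8, the place for changes to protocol-specified analyses, shows no readable text. The SAP history also lists a Section 10 that is not visible.

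**The concern.** The stated target is the chance that a participant has an injection-site AE. The stated model has a mean event count, λ, as its parameter. The two can be linked only through choices the plan does not make: whether each participant contributes 0/1 or a count, whether there is an offset for injections received, what the prior is, and how λ becomes a probability.

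This is the only model-based analysis planned for local tolerability. Injection-site events led to the temporary hold in February 2021 and to the replacement of 75 mg by 15 and 25 mg (Protocol, Amendment 4 rationale). The reported probability will be read beside the MRI result when the benefit-risk balance of the two doses is judged. It should not depend on coding chosen after the data are seen.

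**Working it through.** The documents give no output of this model, so there is no planned figure to reproduce. The check takes each coding that fits the protocol sentence and compares it with a participant-level binomial estimate. Arm size is taken as 15 (45 randomized 1:1:1). Counts are illustrative, and a Jeffreys prior is assumed where an interval is shown, because the plan states none.

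**Reading 1: yes/no outcome, converted by P = 1 - exp(-λ).** With 0/1 data and treatment as the only factor, the fitted λ equals the observed proportion p, before any prior shrinkage. The reported probability is then 1 - exp(-p):

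| True proportion | Reported |
|---|---|
| 10% | 9.5% |
| 20% | 18.1% |
| 30% | 25.9% |
| 50% | 39.3% |
| 75% | 52.8% |

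The risk is always understated, by little when it is low and by a lot when it is high.

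**Reading 2: yes/no outcome, λ read directly as the risk.** The point estimate is right: 10 of 15 gives λ = 10/15 = 67%. The interval is not. The Poisson variance is λ, whereas that of a yes/no outcome is p(1 - p), and λ has no upper bound at 1.

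- Poisson, 10/15: λ ~ Gamma(10.5, rate 15), 90% interval 0.386 to 1.089, that is 39% to 109%.
- Beta-binomial, 10/15: p ~ Beta(10.5, 5.5), 90% interval 46% to 83%.

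At a lower rate the difference shrinks. For 3/15, Gamma(3.5, rate 15) gives 7% to 47% and Beta(3.5, 12.5) gives 8% to 40%.

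**Reading 3: events counted, converted by 1 - exp(-λ).** The conversion assumes that events are spread over participants as a Poisson variable. If the same participants react at each injection, they are not.

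- Illustration: 4 of 15 participants react at all three injections, giving 12 events. λ = 12/15 = 0.80, and 1 - exp(-0.80) = 55%. The proportion affected is 4/15 = 27%.
- In the opposite case, with independent reactions and at most one event per injection, the result errs low. At 25% per injection, λ = 3 × 0.25 = 0.75, which gives 52.8%, while the true probability is 1 - 0.75³ = 57.8%.

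So the direction of the error, and not only its size, depends on coding and clustering that the plan leaves open.

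**Binomial comparator.** A binomial or logistic model with one treatment factor returns the observed proportion in each arm before shrinkage, and its interval stays between 0 and 100%.

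**The case against.** Much of the case on the other side stands.

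- **The planned doses may give low rates.** Amendment 4 puts local tolerability AEs at 15 and 25 mg only 5% and 10% above placebo, and Protocol 1.3.1 describes reactions as rarer and milder in the lower dose groups. At 10% to 20% the yes/no readings lose little. But the placebo rate behind those differences is not given, and this trial gives three injections where the first-in-human study gave one, so low rates cannot be assumed.
- **Participant-level tables are already planned.** SAP 5.1 gives n (%) by preferred term and maximum severity. What is missing is the grouped total, and it can be derived from data already collected.
- **Safety decisions do not use this model.** The stopping rules in Protocol 9.1.5 and 9.1.6 count affected subjects, and the study is exploratory.
- **The SAP may not be silent.** Unreadable Sections 8 and 10 could hold the definition or record that the model was dropped, for example with the move to an abbreviated study report.

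A reader might infer four stronger points that the documents do not support:

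- **That the model would return 53% and 63%** at the first-in-human 40 and 75 mg rates, where "75% and 100% of subjects, respectively, reported any adverse injection site reaction". That requires Reading 1, which the protocol does not state. The rates also come from single doses in four active subjects each, and neither dose is a current randomized arm.
- **That one reaction would be counted several times**, because "The most frequent AEs were injection site warmth, discomfort or pain, or related terms". Protocol 10.1.1.1 asks for a diagnosis in preference to separate signs and symptoms where possible.
- **That the model would rank the doses wrongly.** This can be made to happen only with invented counts, and only if the participant rather than the injection is taken as the proper unit.
- **That Amendment 4's 45% excess at 75 mg exposes an inconsistent placebo rate.** This would combine a model-based difference, a raw proportion and a different endpoint (any AE suspected to be related).

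**Conclusion.** The point holds as a mismatch between target and model, together with a missing definition. It is more than absent detail: when reactions are common, each plausible coding of the Poisson model does worse than a binomial model for the quantity the protocol names. One coding does recover the correct point estimate, so it would be too strong to say that every reading gives a wrong answer; there the fault is in the interval.

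The size is conditional. It is about 2 percentage points at a true risk of 20% and 11 at 50% under Reading 1. Under Reading 2 the upper limit is 109% instead of 83% for 10 of 15. Under Reading 3 the estimate is 55% instead of 27% in the clustered illustration. These figures rest on 15 per arm, assumed counts and, for the intervals, an assumed Jeffreys prior. If reactions are uncommon at 15 and 25 mg, the practical effect of the yes/no readings is small. The finding that the definition and model are absent applies only to the readable SAP.

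**What to change.** In SAP 5.1, make the participant the unit. Report per arm the n (%) with at least one treatment-emergent injection-site or index-knee local reaction, by maximum severity. List the MedDRA terms that count, and draw them from the dictionary rather than from the trial's AE listing, since Protocol 6.4 allows sponsor staff access to treatment assignments during the study.

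If a Bayesian estimate is kept, replace the Poisson regression with a binomial model (beta-binomial or logistic) and state the prior. If the Protocol 12.5.2 model has been dropped, record that and the reason in SAP Section 8; if the definition already sits in the unreadable part, a cross-reference from SAP 5.1 is enough for that item.

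The cost is a few lines of SAP text, one term list and one table from AE data already collected, with no new visits, data or participants.
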